8.4.1. Patient Discontinuation Criteria

Discontinuation refers to a patient's stopping administration of study drug. Reasons for study drug discontinuation may include the following:

- Confirmed clinical worsening event
- Occurrence of an AE or change in medical status that leads the investigator to be concerned about the patient's welfare
- Administrative reasons (*e.g.*, inability to continue)
- Sponsor termination of the study
- Voluntary withdrawal
- Females who become pregnant during the study
- Investigator unblinding

Patients must discontinue study drug if any of the following occur.

- ALT or AST > 8X ULN;
- ALT or AST > 5X ULN for 14 days;
- ALT or AST > 3X ULN and (total bilirubin > 2X ULN or INR > 1.5);
- ALT or AST > 3X ULN with the appearance of fatigue, nausea, vomiting, right upper quadrant pain or tenderness, fever, rash, and/or eosinophilia (> 5%);

Patients who are discontinued from study drug should still continue in the study, completing all study visits and undergo all scheduled study assessments, if possible.

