9.10.5. Current PAH Background Medications

The name, dose, and frequency must be recorded for all PAH background medications that the patient is taking. PAH background medications are those that have been approved by the FDA or the local health authority for the treatment of PAH. Trade or generic drug names should be used where possible. PAH background medications will be reviewed as indicated in [Table 3](#) and all changes will be recorded. Additional background PAH medications may only be prescribed after a clinical worsening event is confirmed.

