12.2.2. Efficacy Variables

The primary efficacy variable is the change from baseline in 6MWD. The secondary efficacy variable is the time-to-first clinical improvement event. [REDACTED]

[REDACTED]

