10.2. Secondary efficacy outcome

The secondary efficacy outcome is the time-to-first persistent clinical improvement event. To declare that clinical improvement has occurred, at least one of the following four criteria must be met:

1. Improvement by at least one WHO functional class coupled with no more than a 15% decrease from baseline in 6MWT.
2. Increase from baseline in 6MWT by at least 10% and stability or improvement in the WHO functional class.
3. Decrease from baseline in creatine kinase (a surrogate biomarker for muscle injury and inflammation) by at least 10% and no worsening in WHO functional class and no more than a 15% decrease from baseline in 6MWT.
4. Improvement in estimated glomerular filtration rate (eGFR) $\geq 10\%$ of baseline.

The persistence of the change in WHO functional class, 6MWT, eGFR, or creatine kinase must be confirmed by a subsequent assessment that also meets the defined criteria. The confirmatory assessment must occur at least 14 days after the initial assessment, or at the next scheduled assessment. If persistent improvement is confirmed, the date of the event will be considered the initial assessment of improved WHO functional class, 6MWT, eGFR, or creatine kinase.

If confirmatory observation of initial improvement is not available for any reason, such as end of study or death, it may or may not be considered an event as defined by the timing of improvement as it relates to other study events. Below is a list of possible reasons for failure to obtain a confirmatory observation along with the adjustment to the definition of improvement.

These reasons are as follows:

1. Last visit: If the improvement is observed at the last scheduled assessment, the requirement for an additional assessment after 14 days is waived, and the patient is classified as satisfying the criteria for improvement. In the absence of study end date, Study Drug Termination (SDT) is used.
2. Death: If the patient's death occurs before the confirmatory observation, then the patient is classified as not satisfying the criteria for improvement.
3. Study termination: If the patient terminates the study for reasons of "lost to follow-up" or "withdrawal of consent", then the patient is classified as not satisfying the criteria for improvement.
4. Patient starts new PAH drug: If a patient decides to stop study drug and switch to a new PAH drug, then the patient is classified as not satisfying the criteria for improvement.

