11. STATISTICAL METHODS

11.1. Primary efficacy outcome

11.1.1. Primary analysis

This section describes the methods planned for the primary analysis, which is based on the primary efficacy outcome, the change from baseline in 6MWT. The analysis will compare the mean change in the bardoxolone methyl group relative to placebo at Week 24. A mixed model will be fit with this outcome using the following PROC MIXED code in SAS, where ID is the patient identifier, SCR_6MWT and DELT_6MWT are the screening values for the 6MWT and change from baseline, respectively, in the primary outcome at each visit (VOBS) by treatment group (GRP), and N_PAH_MEDS is the fixed number of background PAH therapies for a patient. Below is example code used to estimate the treatment effect:

```
proc mixed data = &DAT. method=reml alpha=0.05 covtest;
  class ID GRP (ref="plc") VOBS (ref=LAST)
    N_PAH_MEDS;
  model DELT_6MWT = SCR_6MWT
                    N_PAH_MEDS
                    GRP
                    VOBS
                    GRP * VOBS
                    VOBS * SCR_6MWT Hb / s ddfm=kr;
  repeated VOBS / subject = ID type = UN r;
  lsmeans VOBS * GRP / diff om cl e;
run;
```

The model will have the following characteristics:

- The response variable will be the vector of observed change in the primary efficacy outcome from baseline at each study visit where the 6MWT is measured (Week 4, Week 8, Week 16, and Week 24). The outcome will consist of the following four repeated measures: Week 4 6MWT – baseline 6MWT, Week 8 6MWT – baseline 6MWT, Week 16 6MWT – baseline 6MWT, and Week 24 6MWT (averaged over both measurements made at Week 24) – baseline 6MWT. [REDACTED] 6MWT values collected after the date of clinical worsening will be treated as missing for analysis of 6MWT.
- Repeated post-baseline measurements from each patient will be identified by patient identifier (ID).
- Within-patient correlations will be modeled using an unstructured covariance structure. In the unlikely situation that this model does not converge (i.e., the study has too few observations for the number of parameters estimated), the model will use the heterogeneous Toeplitz structure, which assumes the correlation between two repeated measurements depends solely on their lag in visit number, and that the variance of the outcome may differ over time. If the model still does not converge

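### On the readable text, an improvement first seen after a PAH drug is added can count in the only secondary endpoint, because rule 4 of SAP 10.2 covers only patients who stop study drug and switch

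*SAP*

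**What the plan says.** Protocol 12.2.2 names one secondary endpoint: "The secondary efficacy variable is the time-to-first clinical improvement event". SAP 10.2 gives four ways to qualify:

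1. a better WHO class, with the walk distance no more than 15% below baseline;
2. a walk distance at least 10% above baseline, with WHO class not worse;
3. creatine kinase at least 10% below baseline, with WHO class not worse and the walk distance no more than 15% below baseline;
4. eGFR at least 10% above baseline, with no further condition.

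The change must be confirmed at a later assessment. The SAP then turns to cases that begin "If confirmatory observation of initial improvement is not available for any reason" and introduces five rules: "Below is a list of possible reasons for failure to obtain a confirmatory observation along with the adjustment to the definition of improvement". Rule 1 waives confirmation at the last scheduled assessment. Rule 4 has a heading about starting a new PAH drug, but its text is narrower: "If a patient decides to stop study drug and switch to a new PAH drug", that patient is classed as not meeting the improvement criteria. Rule 5 concerns stopping study drug for an adverse event and accepts an improvement that is confirmed.

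On conduct, Protocol 9.10.5 states: "Additional background PAH medications may only be prescribed after a clinical worsening event is confirmed". Protocol 8.4.1 lists confirmed clinical worsening among possible, not mandatory, reasons to stop study drug, and adds: "Patients who are discontinued from study drug should still continue in the study". For the primary analysis, SAP 11.1.1 states: "6MWT values collected after the date of clinical worsening will be treated as missing for analysis of 6MWT".

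**The concern.** The endpoint is meant to show what randomised treatment does for function. A patient who worsens, is given a further approved PAH drug and then improves has an improvement that cannot be separated from that drug. Rule 4 shows that the sponsor does not want to credit such an improvement when the patient switches. The readable text does not extend this to the patient who adds a drug and continues study drug, although the protocol allows that course.

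Two things are at stake. First, events may be credited to an arm because of a drug given after treatment failed there. If more placebo than active patients have a drug added, this pulls the hazard ratio toward 1. Second, the heading, the text and the list introduction of rule 4 give three different scopes, so two programmers could derive different events from the same data.

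**Working it through.** **Step 1. Follow one patient through the text.** Suppose a patient has confirmed worsening at Week 6, adds a PAH drug, stays on study drug, and at Weeks 16 and 24 walks at least 10% above baseline with WHO class no worse than at baseline.

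- The addition is allowed (Protocol 9.10.5), and stopping study drug is optional (Protocol 8.4.1).
- Criterion 2 is met at Week 16 and confirmed at Week 24.
- Rule 4 does not apply, because the patient neither stopped nor switched.
- Result on the readable text: an event dated Week 16. If the improvement first appears at the last scheduled assessment, rule 1 makes it an event without confirmation.

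**Step 2. Does rule 4 reach confirmed improvements?** The list is introduced as covering missing confirmation, which suggests that it does not. Rule 4 itself carries no such condition, and rule 5 in the same list decides a confirmed case, which suggests that it may. Both readings leave a problem. On the narrow one, a patient who switches, stays in follow-up and is confirmed escapes the rule. On the broad one, rule 4 has no timing condition and would erase an improvement confirmed before the switch. It would also conflict with rule 5 for a patient who stops because of disease progression recorded as an adverse event (Protocol 11.6), switches, and has a confirmed improvement.

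**Step 3. Does the SAP 11.1.1 rule apply here?** It is worded for analysis of the walk test and stands in the primary analysis section. The readable SAP does not say that it carries over. If it does, criteria 1, 2 and 3 all need a walk value that would be missing after worsening, and only criterion 4 (eGFR) clearly remains open.

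**Step 4. Size.** The plan gives no readable event rate, hazard ratio or power for this endpoint, so there is no figure to reproduce. All rates below are assumptions. From the documents: about 130 patients, 1:1, so 130/2 = 65 per arm, and a two-sided test.

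Let p be the proportion with an event by Week 24 without added therapy, r the share of event-free patients who have a PAH drug added, and q the share of those who then meet a criterion. Then p' = p + (1 − p)·r·q, HR = ln(1 − p'_active)/ln(1 − p'_placebo), and power = Φ(√(D/4)·ln HR − 1.96) with D = 65·(p'_active + p'_placebo).

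Worked case with p = 0.50 placebo and 0.65 active, r = 0.15 and 0.05, q = 0.6:

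- Before: HR = ln 0.35/ln 0.50 = 1.51; D = 74.75; power 43%.
- Placebo: 0.50 + 0.50 × 0.15 × 0.6 = 0.545, or 2.9 extra events.
- Active: 0.65 + 0.35 × 0.05 × 0.6 = 0.6605, or 0.7 extra events.
- After: HR = ln 0.3395/ln 0.455 = 1.37; D = 78.4; power 29%.

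| p placebo / active | r placebo / active | q | HR before → after | Power before → after |
|---|---|---|---|---|
| 0.50 / 0.65 | 0.05 / 0.02 | 0.3 | 1.51 → 1.49 | 43% → 41% |
| 0.50 / 0.65 | 0.10 / 0.05 | 0.6 | 1.51 → 1.43 | 43% → 35% |
| 0.50 / 0.65 | 0.15 / 0.05 | 0.6 | 1.51 → 1.37 | 43% → 29% |
| 0.60 / 0.75 | 0.05 / 0.02 | 0.3 | 1.51 → 1.50 | 49% → 47% |
| 0.60 / 0.75 | 0.15 / 0.05 | 0.6 | 1.51 → 1.40 | 49% → 36% |

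**Step 5. A harsher variant and a balanced one.** Assume that worsened patients never improve before the addition, that 40% of other placebo patients improve, and that the hazard ratio among non-worsening patients is 1.6, which gives 1 − 0.6^1.6 = 0.558 on active.

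- Worsening 15% placebo, 5% active, later improvements not counted: ln(1 − 0.95 × 0.558)/ln(1 − 0.85 × 0.40) = 1.82.
- The same, counted: 1.62 (q = 0.3) to 1.46 (q = 0.6).
- Worsening 10% in each arm: 1.56 becomes 1.54 to 1.52, a shift of at most 0.05.

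**The case against.** The strongest reply is that the rule may already exist. SAP 11.2 calls the outcome censored and contains redacted blocks where a censoring rule could stand. This holds as a limit: a reader might infer that the plan does count these improvements, and the documents do not establish that. What can be said is that the readable definition in SAP 10.2, where the classification is made, does not exclude them.

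A second reply is that rule 4 is not confined to unconfirmed improvements, since rule 5 decides a confirmed case. That also holds. The scope of rule 4 is unclear; the text does not show it to be narrow.

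A third is that counting every assessment whatever is added is a recognised treatment-policy choice and fits the ITT population. It is, but rule 4 departs from that policy for switchers, and the readable plan gives no reason to treat patients who add a drug differently.

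A fourth is that the numbers are small. This is a first-event endpoint, and functional class, creatine kinase and creatinine are assessed from Week 1, so many patients may have their event before any addition. Additions are also discouraged (Protocol 8.1, criterion 8). This limits the size and leaves the gap in the definition.

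Three stronger readings are tempting and should not be adopted:

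- That functional class and creatine kinase would still count if the SAP 11.1.1 rule carried over. Criteria 1 and 3 also need a walk value.
- That fluid overload would make the active arm worsen more and have its failures scored as successes. Protocol 5.1.2 describes that risk in Stage 4 CKD and says it has not been observed in PAH patients to date.
- That the endpoint moves against the clinical truth whichever arm worsens more. With more worsening on placebo, the calculated effect is attenuation and still favours active. In the reverse case (15% active, 5% placebo, no true effect on improvement), the harsher variant moves 0.87 to 0.97 or 1.07, passing 1 only at the higher response rate.

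**Conclusion.** The point holds in limited form. On the readable text, a patient who adds a PAH drug after confirmed worsening and stays on study drug can be counted as improved on assessments made after the addition. Whether rule 4 applies to confirmed improvements, and whether the SAP 11.1.1 rule reaches this endpoint, is not stated.

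The size depends on how often PAH therapy is added and how far this differs by arm, and the documents give neither. Under the assumed rates in Step 4 the effect is attenuation, from 1.51 to between 1.37 and 1.50, with a loss of about 2 to 15 points of power. It is small if additions are rare or balanced. Because this is the only secondary efficacy endpoint and the ambiguity affects how events are derived, it should be settled before unblinding.

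**What to change.** Before database lock, reword rule 4 so that its text matches its heading, for all four criteria and whether or not a confirmatory observation exists:

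- An assessment made after the start of any new or additional PAH therapy, with or without stopping study drug, can neither start nor confirm an improvement event.
- An improvement confirmed before that start still counts.
- A patient not already confirmed is classified as not satisfying the criteria, as rule 4 already does for switchers.
- This rule takes precedence over rule 5 and over the last-visit waiver in rule 1.

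Also state whether the SAP 11.1.1 post-worsening rule applies to this endpoint, and give the censoring time for these patients if the redacted text does not. Report as supplementary an analysis that counts all assessments regardless of new PAH therapy.

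The change does not align the endpoint with the primary analysis: SAP 11.1.1 sets later walk values to missing, whereas this rule treats the patient as not improved. Its justification is consistency with rule 4. The cost is SAP wording and a few lines of derivation code, since PAH medication changes are already recorded (Protocol 9.10.5), and a few events are lost.

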10.3. Exploratory efficacy outcomes

[REDACTED]

- 1. [REDACTED]
 - 1. [REDACTED]
 - 2. [REDACTED]
- 2. [REDACTED]
- 3. [REDACTED]
- 4. [REDACTED]
- 5. [REDACTED]

[REDACTED]

- 1. [REDACTED]
- 2. [REDACTED]
- 3. [REDACTED]
- 4. [REDACTED]

- [REDACTED]
- [REDACTED]
- [REDACTED]
- [REDACTED]

[REDACTED]

[REDACTED]

[REDACTED]

[REDACTED]

[REDACTED]

11. STATISTICAL METHODS

11.1. Primary efficacy outcome

11.1.1. Primary analysis

This section describes the methods planned for the primary analysis, which is based on the primary efficacy outcome, the change from baseline in 6MWT. The analysis will compare the mean change in the bardoxolone methyl group relative to placebo at Week 24. A mixed model will be fit with this outcome using the following PROC MIXED code in SAS, where ID is the patient identifier, SCR_6MWT and DELT_6MWT are the screening values for the 6MWT and change from baseline, respectively, in the primary outcome at each visit (VOBS) by treatment group (GRP), and N_PAH_MEDS is the fixed number of background PAH therapies for a patient. Below is example code used to estimate the treatment effect:

```
proc mixed data = &DAT. method=reml alpha=0.05 covtest;
  class ID GRP (ref="plc") VOBS (ref=LAST)
    N_PAH_MEDS;
  model DELT_6MWT = SCR_6MWT
                    N_PAH_MEDS
                    GRP
                    VOBS
                    GRP * VOBS
                    VOBS * SCR_6MWT Hb / s ddfm=kr;
  repeated VOBS / subject = ID type = UN r;
  lsmeans VOBS * GRP / diff om cl e;
run;
```

The model will have the following characteristics:

- The response variable will be the vector of observed change in the primary efficacy outcome from baseline at each study visit where the 6MWT is measured (Week 4, Week 8, Week 16, and Week 24). The outcome will consist of the following four repeated measures: Week 4 6MWT – baseline 6MWT, Week 8 6MWT – baseline 6MWT, Week 16 6MWT – baseline 6MWT, and Week 24 6MWT (averaged over both measurements made at Week 24) – baseline 6MWT. [REDACTED] 6MWT values collected after the date of clinical worsening will be treated as missing for analysis of 6MWT.
- Repeated post-baseline measurements from each patient will be identified by patient identifier (ID).
- Within-patient correlations will be modeled using an unstructured covariance structure. In the unlikely situation that this model does not converge (i.e., the study has too few observations for the number of parameters estimated), the model will use the heterogeneous Toeplitz structure, which assumes the correlation between two repeated measurements depends solely on their lag in visit number, and that the variance of the outcome may differ over time. If the model still does not converge

with the heterogeneous Toeplitz structure, the model will use a homogeneous Toeplitz structure. Finally, if the model using the homogeneous Toeplitz structure does not converge, the model will use a compound symmetry structure which assumes equal correlation for a patient's measurements, regardless of how far apart in time they were taken.

- The models will include the following covariates:
 - Time defined as a categorical variable (i.e., no restriction is imposed on the trajectory of the mean outcome over time) (VOBS)
 - Treatment group (GRP)
 - N_PAH_MEDS (stratification variable for number of background PAH therapies)
 - Screening 6MWT (SCR_6MWT)
 - Screening 6MWT by time interaction (VOBS * SCR_6MWT)
 - Day 1 hemoglobin (Hb)
 - Time by treatment group interaction (GRP * VOBS)

The MMRM, as defined above, uses the screening value of the 6MWT as a covariate and the baseline value of the 6MWT for the computation of the outcome (the change from baseline). This allows adjustment for the “baseline” value between groups while providing the ability to provide valid estimates of the placebo-adjusted treatment effect.

In the event the MMRM model with an unstructured covariance structure does not converge, the following covariance structures are substituted, in the order listed. Each subsequent covariance structure is used only if each previous covariance structure is used and no previous model converged.

1. Heterogeneous Toeplitz covariance structure (assuming different variances at each time point and that measurements taken closer together in time are more highly correlated than those taken farther apart).
2. Toeplitz covariance structure (assuming measurements taken closer together in time are more highly correlated than those taken farther apart).
3. First order auto-regressive [AR(1)] covariance structure (assuming measurements taken closer together in time are more highly correlated than those taken farther apart, but the correlation is more constrained than the Toeplitz structure).
4. Compound symmetry covariance structure (assuming equal correlation for measurements from a patient, regardless of how far apart in time they were taken). A compound symmetry covariance structure was assumed in the sample size calculation.

Results of MMRM are summarized in tables and line plots. Additionally, line plots of 6MWT change from baseline, labeled by treatment group up to and including Week 24 are generated

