- k A serum pregnancy test will be performed at the Screening visit for WOCBP or at any point in time if a pregnancy is suspected. All other pregnancy assessments will be urine pregnancy tests. Additional pregnancy assessments will be performed more frequently if required by local law or if requested by a local health authority or IRB/EC. For WOCBP enrolled in the UK and Argentina, pregnancy testing will be performed every 4 weeks while taking study drug.
- l AE assessments on Day 1 should be performed following study drug administration.
- m [REDACTED]
- n [REDACTED]
- o [REDACTED]
- p [REDACTED]
- q [REDACTED]
- r Patients must be instructed to not take their study drug prior to coming to the clinic for visits when PK samples will be collected. Patients must administer the study drug dose in the clinic on PK sample collection visits after the 0 hour PK blood sample is collected. Patients will have blood samples for PK analysis drawn just prior to (0 hour) and after (2 and 4 hours) dose administration.
- s Patients participating in the PK sub-study will have 5 additional blood samples for PK analysis drawn for this visit. PK sub-study patients will have blood samples for PK analysis drawn just prior to (0 hour) and after (1, 2, 3, 4, 6, 8, and 24 hours) dose administration for this visit.
- t Patients not participating in the PK sub-study may have blood collected on either day of the Week 24 visit.
- u The 6-minute walk test must be performed on two separate days within the 3-day window at Week 24.
- v Patients who terminate from the study prior to the Week 24 study visit should be brought back to the clinic as soon as possible for early termination assessments (*i.e.*, Week 24 Day Prior and end-of-treatment visits) as well as a follow-up visit 4 weeks later. Patients should complete the end-of-treatment procedures, including the 6MWT, prior to any adjustments being made to their PAH treatment regimen.

Abbreviations: ECG = electrocardiogram, PK = pharmacokinetic, V/Q = ventilation-perfusion, WOCBP = women of child-bearing potential, 6MWT = 6-minute walk test, [REDACTED]

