5. GENERAL CONVENTIONS

The protocol-specified time windows for a visit ([Appendix D](#)) and time of a measurement (Section [5.4](#)) determine the visit assignment for each observation.

Continuous data will be summarized using descriptive statistics: number of observations (n), mean, median, standard deviation (SD), minimum, and maximum. Confidence intervals (CIs) will be presented as appropriate. The same number of decimal places as in the observed value will be presented when reporting minimum and maximum; 1 more decimal place than in the observed value will be presented when reporting mean and median; and 2 more decimal places than in the observed value will be presented when reporting SD. When values are averaged in the analysis data (e.g., in the calculation of baseline), the same number of decimal places as in the observed value will be presented.

Frequencies and percentages will summarize categorical data. Presentations of categorical data will generally suppress percentages for items where the count is zero in order to draw attention to nonzero counts.

Confidence intervals will generally be constructed at the 95% level. For binomial variables, exact methods will be employed unless otherwise specified.

Categorical/qualitative data will be presented using frequency counts and percentages. All percentages will be rounded to 1 decimal place, unless otherwise specified. Percentages equal to 100 will be presented as 100% and no percentages will be presented for zero frequencies.

Summary presentations will classify patients by their randomized treatment group for analyses on the ITT population, and actual treatment received for analyses on the safety population, unless otherwise specified. References to treatment group from this point forward in the SAP text indicate randomized treatment group, unless stated otherwise.

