5.2. Definition of scheduled post-baseline measurements

Instead of relying solely on visit labels in the clinical database for post-baseline values, results collected on a date will be attributed to a specific time point by calculating the days relative to randomization. Listings will present all measurements.

Section 5.4 describes how time is calculated for each assessment.

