5.2.2. Non-laboratory parameters

Post-baseline measurements of non-laboratory parameters are defined as the measurements collected on the day closest to the patient’s target visit day ([Appendix D](#)). If two assessments are equidistant from a target study day, the earlier assessment is used. If the visit used for analysis includes two assessments on the same day, the average of the two measurements will be used. The last clinic visits on and off study drug will be classified according to when they occurred as specified in [Section 5.2.3](#).

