5.2.3. Last clinic visit and post-treatment results

Patients who terminate from the study before the Week 24 study visit should be brought back to the clinic as soon as possible for early termination assessments as well as a follow-up visit four weeks later. All assessments through Week 24 will be classified according to the time relative to randomization, regardless of the patient’s study participation or study drug status. Post treatment assessments will be classified according to the time relative to last dose in [Appendix D](#), for example 4 weeks off-treatment is within 7 to 35 days after last dose of the study.

Patients who discontinue treatment early but continue to be followed until the end of study will have their assessments attributed to visits as specified in [Section 5.2.1](#) and [Section 5.2.2](#).

A listing will indicate when each patient’s visits occurred. [Appendix D](#) indicates how scheduled results will be classified.

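### The only visible visit-window table gives walks on Days 2–21 and 36–49 no level in the primary MMRM, so such 6MWTs drop out of the primary analysis

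*SAP*

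**What the plan says.** SAP 11.1.1 defines the response as the change in 6MWT "at each study visit where the 6MWT is measured (Week 4, Week 8, Week 16, and Week 24" and adds that "The outcome will consist of the following four repeated measures", one for each of those weeks.

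The visit that a walk belongs to is set by date. SAP 5 has the Appendix D windows and the time of measurement "determine the visit assignment for each observation". SAP 5.2 does not leave this to the database labels alone; under its rule, "results collected on a date will be attributed to a specific time point by calculating the days relative to randomization". SAP 5.2.2 covers the 6MWT as a non-laboratory measure: "Post-baseline measurements of non-laboratory parameters are defined as the measurements collected on the day closest to the patient’s target visit day", with target days again taken from Appendix D. No separate list of 6MWT target days is visible.

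Table D 1 in Appendix D has rows for Weeks 1, 2, 4, 6, 8, 16 and 24. A further Week 28 row is restricted by footnote to the eGFR analysis.

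For patients who leave the study before Week 24, footnote v to Protocol Table 3 says they "should be brought back to the clinic as soon as possible for early termination assessments", which include the 6MWT, with a follow-up visit four weeks later. SAP 5.2.3 then says "All assessments through Week 24 will be classified according to the time relative to randomization", whatever the patient's drug or study status. The next sentence of SAP 5.2.3 classes post-treatment assessments by time since last dose.

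**The concern.** The window table has seven on-treatment visits and the model has four. A walk whose date falls in a Week 1, Week 2 or Week 6 window gets a label that the MMRM does not contain. No visible rule moves it to a modelled visit. The plan foresees walks on such days, because it asks for a 6MWT at early termination whenever that happens.

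At stake is collected primary-endpoint data. A patient who leaves on Days 2–21 would usually have no other walk on treatment and could contribute nothing to the MMRM, although SAP 3.1 defines the ITT population as all randomized patients. A patient who leaves on Days 36–49 would usually keep a Week 4 value and lose the last walk. Protocol 12.3.1 planned a tipping-point check of the missing-at-random assumption, but the SAP revision history records that the multiple-imputation sensitivity analyses were removed. That is one more reason not to discard observed outcomes.

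**Working it through.** The question is one of mapping. The planned size of about 130 (65 per group, SAP Appendix B.2) is not in dispute, and it cannot be reproduced because its inputs are redacted.

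**1. Map each window (SAP Table D 1) to the model (SAP 11.1.1).**

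| Days | Target day | Label | In the MMRM? |
|---|---|---|---|
| 2–10 | 7 | Week 1 | no |
| 11–21 | 14 | Week 2 | no |
| 22–35 | 28 | Week 4 | yes |
| 36–49 | 42 | Week 6 | no |
| 50–84 | 56 | Week 8 | yes |
| 85–139 | 112 | Week 16 | yes |
| 140–182 | 168 | Week 24 | yes |

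**2. Count the gaps.** Days 2–21 are 21 − 2 + 1 = 20 days. Days 36–49 are 49 − 36 + 1 = 14 days. The total is 34. From Day 2 to Day 168 there are 167 days, so the share is 34/167 = 20.4%.

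**3. Repeat with the nearest-target rule of SAP 5.2.2.** Midpoints between neighbouring targets are (14 + 28)/2 = 21, (28 + 42)/2 = 35 and (42 + 56)/2 = 49. With ties to the earlier target, the same 34 days are lost.

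**4. Check on-time walks.** The protocol windows are 28 ± 3 (25–31), 56 ± 3 (53–59), 112 ± 3 (109–115) and, for the two Week 24 days, 167 ± 3 and 168 ± 3 (164–171). All map to the right modelled visit.

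**5. How far off schedule must a walk be?** A Week 4 walk falls in the Week 6 window if it is 36 − 28 = 8 to 49 − 28 = 21 days late. A Week 8 walk does so if it is 56 − 49 = 7 to 56 − 36 = 20 days early.

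**6. Follow-up walk after early termination on Day T, at T + 28.** SAP 5.2.3 supports two readings.

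- By time from randomization: T = 2–7 gives Days 30–35 (Week 4); T = 8–21 gives Days 36–49 (Week 6, not modelled); T = 36–49 gives Days 64–77 (Week 8).
- By time from last dose: the walk is an off-treatment assessment about 28 days after the last dose and has no level in the model.

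The early-termination walk itself, for T in the gaps, is outside the model on both readings.

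**7. Scale.** The documents give no visible early-termination rate. Assume that a share p of 130 patients terminates early, uniformly over Days 2–168, and that each has a termination walk. Expected walks in the gaps are 130 × p × 34/167; those on Days 2–21 are 130 × p × 20/167.

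| p | In either gap | On Days 2–21 |
|---|---|---|
| 5% | 1.3 | 0.8 |
| 10% | 2.6 | 1.6 |
| 20% | 5.3 | 3.1 |
| 30% | 7.9 | 4.7 |

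**8. Upper bound on power.** Assume a design power of 80% or 90% at two-sided 0.05 with 65 per group. The standardized effect is then d = (1.960 + z)/√(65/2) = 0.491 or 0.569, where z is the normal quantile of the assumed power. Losing all 5.3 patients leaves 65 − 5.3/2 = 62.35 per group, and Φ(d√(62.35/2) − 1.960) gives 78.3% or 88.8%. The loss is below two points.

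**The case against.** Much of the case on the other side is sound and limits the point.

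- **Retests.** A reader might infer that repeats of partial walks are lost too. SAP 5.3 says that retests of partial walks stopped for non-medical reasons will be used, so this does not follow.
- **Off-drug walk replacing the end-of-treatment walk.** A reader might infer that a patient who leaves on Days 36–49 has the off-drug follow-up walk counted as Week 8. That is one reading of SAP 5.2.3. The sentence on time since last dose supports another, in which the walk is not modelled. The text is unclear; it does not establish the substitution.
- **Who has an early-termination walk.** Under Protocol 8.4.1, patients who stop drug should stay and attend all visits, so their walks remain on schedule. Protocol 8.4.2 lists loss to follow-up, death and withdrawal of consent as reasons for termination. The first two give no walk. The rates in the working are therefore generous.
- **Loss differing by arm.** A reader might point to the three-to-four-week fluid-overload risk in Protocol 5.1.2. That finding comes from Stage 4 CKD with type 2 diabetes, and the same section says the risk has not been observed in PAH patients to date. Differential loss is possible but not shown.
- **Size.** A reader might note that 34 of the 48 days from Day 2 to Day 49 (71%) fall in the gaps. That counts calendar days, and no walk is scheduled on any of them.
- **Other text.** SAP 5.2 leaves visit labels some role, and part of SAP 11.1.1 is redacted. Some of these walks would be set to missing anyway under the clinical-worsening rule.
- **Very early walks.** Leaving a walk from the first days out of a Week 24 comparison is defensible.

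What remains is that nothing visible assigns a termination walk or a badly mistimed walk in the gaps to a modelled visit. The plan should decide this openly and not leave it as a by-product of the laboratory schedule.

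**Conclusion.** The point holds as a cheap improvement. As written, 6MWTs on Days 2–21 and 36–49 have no level in the primary MMRM. The walks at risk are early-termination walks and walks well outside the ±3-day windows.

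The effect is probably small: about 1–5 of 130 patients if 5–20% terminate early at uniform times. Both the rate and the uniform timing are assumptions, and so is a walk for every leaver. The cost in power is minor. The reason to act is selective loss of collected primary-endpoint data from early leavers. The direction of any bias cannot be worked out from the documents, and they do not support a claim that the primary result would be biased for or against the drug.

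Two related ambiguities belong with it. SAP 5.2.3 gives two clocks for a follow-up walk after early termination. Table D 1 counts from first dose, while SAP 5.2, 5.2.3 and 5.4 count from randomization; the two agree when both fall on Day 1, as Protocol 9.10.2 expects.

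**What to change.** Add a 6MWT-only window table to Appendix D and state in SAP 11.1.1 that the primary MMRM uses it:

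- Week 4: up to Day 42, the midpoint (28 + 56)/2, with a stated and justified lower limit
- Week 8: Days 43–84
- Week 16: Days 85–139
- Week 24: Days 140–182

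Keep the rule that the walk closest to the target day is used. Fix the lower limit of Week 4 before unblinding. At Day 2, no day up to Day 182 lacks a level. At the present Day 22, the 20 days from Day 2 to Day 21 stay out, but by stated choice.

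State that an off-treatment follow-up walk does not replace an end-of-treatment walk. The new windows do not settle this alone. If follow-up walks were timed from randomization, termination on Days 36–42 would give a follow-up walk on Days 64–70, labelled Week 8. With a lower limit of Day 2, a follow-up walk at T + 28 lies T days from target Day 28 and the termination walk 28 − T days, so the follow-up walk would win for T below 14.

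Use one day origin throughout.

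The cost is one short table and a derivation step, with no new data. On-time patients are unchanged, because their scheduled walk is still the closest. There are two downsides. Some walks are labelled two weeks or more from their nominal visit, including walks on Days 36–42 that come after the scheduled Week 4 escalation. And not every walk is recovered: one on Days 36–42 still yields to an on-time Week 4 walk, and a Week 4 walk 15–21 days late (Days 43–49) still yields to an on-time Week 8 walk.
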